3.5.4 Analysis Populations

For fracture endpoints a "Full-Analysis-Set" (FAS) population will be used. This will include all randomized patients, who took at least one dose of study medication, with follow-up from Randomization to study termination, without regard to protocol violations, compliance to study drug or early treatment discontinuation. Patients will be counted in the treatment group they were randomized to, irrespective of the treatment they actually received.

All available scans to determine morphometric vertebral fractures, will be used in the analyses. For morphometric fractures, a patient with no scan during the study will not be included in the FAS population. For the final analysis of clinical fractures, a calendar date (cut-off) will be determined when the pre-specified number of fracture events are seen. For the analysis of clinical fractures, patients who did not have a fracture by the time of the cut-off date will be censored at the cut-off date, unless they discontinued the study earlier, then they will be censored at the date of the last contact with the patient (either

Product: MK-0822

46

Protocol/Amendment No.: 018-04

telephone contact or study visit). Clinical fractures after the cut-off date will not be included in the analysis.

As a supportive approach, vertebral, non-vertebral and hip fracture analyses will also be performed based on the "Per-Protocol" (PP) population, to investigate the influence of missing data and protocol violators on the treatment effect. This approach excludes patients from the FAS population if they have important protocol deviations. Specific criteria to exclude a patient are identified in appendix 6.7, prior to unblinding of study database and will be based on a patient's compliance to study medication, the use of prohibited previous or concomitant medication, and the presence of secondary diagnoses which may influence the efficacy results. Data will be censored at the date of the last dose of study medication plus 30 days, for patients who did not have a clinical fracture by that time. The per-protocol analysis will not be performed if less than 10% patients (included in the FAS approach) are protocol violators.

A similar FAS population will be used as the analysis approach for BMD endpoints and stature, including all randomized patients who took at least one dose of study medication and have the necessary on-treatment information. Missing data will be handled by the longitudinal model, therefore no imputation of missing data will be necessary. As indicated in appendix 6.7, BMD measurements taken more than 30 days after the last dose of study medication will primarily not be included in the analyses, for results to be consistent with those from phase IIb and future phase III studies. For consistency with the approach for fracture endpoints, a supportive analysis including these measurements taken long after the last dose will also be performed.

The analyses of biochemical markers of bone turnover and formation will be performed using the per-protocol approach. BMD at the total body and distal forearm and biochemical marker endpoints will only be performed for approximately 10% of the randomized patients.

Time to first major cardiovascular and cerebrovascular event will be handled similarly as clinical fractures and will be based on the FAS approach.

Summary tables for health resource and meal questionnaires and bone biopsies will be for the FAS population.

Safety analyses will be based on the "All-Patients-as-Treated" (APaT) population, which includes all randomized patients who received at least one dose of study medication. For safety analyses, patients will be included in the treatment group for the treatment they actually received. For safety analyses, missing data will not be imputed.

Product: MK-0822

47

Protocol/Amendment No.: 018-04

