2.1.2 Secondary

- (1) **Objective:** To assess the effect of treatment with odanacatib 50 mg once weekly on the risk of clinical vertebral fractures compared to placebo.

Hypothesis: Treatment with odanacatib reduces the risk of clinical vertebral fractures compared to placebo.

- (2) **Objective:** To assess the effect of treatment with odanacatib 50 mg once weekly on height compared to placebo.

Hypothesis: Treatment with odanacatib reduces height loss compared to placebo.

- (3) **Objective:** To assess the effect of treatment with odanacatib 50 mg once weekly on the lumbar spine, total hip, femoral neck, trochanter and distal forearm BMD compared to placebo.

Hypothesis: Treatment with odanacatib increases lumbar spine, total hip, femoral neck, trochanter, and distal forearm BMD compared to placebo.

Product: MK-0822

8

Protocol/Amendment No.: 018-04

- (4) **Objective:** To assess the safety and tolerability of treatment with odanacatib 50 mg once weekly compared to placebo.

Hypothesis: Odanacatib is safe and well tolerated compared to placebo.

- (5) **Objective:** To assess the effect of treatment with odanacatib 50 mg once weekly on biochemical indices of bone resorption (serum C-Telopeptides of Type 1 collagen [s-CTx] and urine N-Telopeptides of Type 1 collagen [u-NTx]) compared to placebo.

Hypothesis: Treatment with odanacatib decreases biochemical indices of bone resorption (s-CTx and u-NTx) compared to placebo.

- (6) **Objective:** To assess the effect of treatment with odanacatib 50 mg once weekly on lumbar spine, total hip, femoral neck, and hip trochanter BMD compared to placebo, in patients who are bisphosphonate-intolerant (i.e. patients with a contraindication or history of intolerance to bisphosphonates, or those considered by their physician to be unsuitable for bisphosphonate treatment).

Hypothesis: Treatment with odanacatib increases lumbar spine, total hip, femoral neck, and hip trochanter BMD compared to placebo in patients who are bisphosphonate-intolerant (i.e. patients with a contraindication to or a history of intolerance of oral bisphosphonate use).

- (7) **Objective:** To assess the effect of treatment with odanacatib 50 mg once weekly on biochemical indices of bone formation (serum bone-specific alkaline phosphatase [BSAP] and serum N-Terminal Propeptides of Type 1 collagen [s-P1NP]) compared to placebo.

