2.4.2 Treatment Plan

2.4.2.1 Blinded Study Therapy and Vitamin D₃

All patients will receive open-label vitamin D₃ (5600 IU once weekly), which will be supplied as two 2800 IU tablets, to be taken once a week. Patients will be randomly assigned to blinded study therapy, either odanacatib (50 mg once weekly) or placebo, and will receive medication according to their assigned treatment group as shown in Table 2-1.

Table 2-1

Sample Allocation Schedule

Treatment Group	Treatment
Odanacatib 50 mg Once Weekly	Odanacatib 50 mg once weekly & 5600 IU Vitamin D ₃ once weekly
Placebo	Placebo once weekly & 5600 IU Vitamin D ₃ once weekly

Vitamin D₃ and odanacatib will be taken without regard to food. Patients are allowed to choose the day of the week on which to take blinded study therapy and vitamin D₃ supplements (the blinded study therapy and open-label vitamin D₃ need not be taken on the same day of the week). Patients must record on diary cards each day that blinded study therapy and study-provided vitamin D₃ is taken.

Patients should be instructed to take one tablet of blinded study therapy once a week (on their choice of day). As stated above, this may be taken without regard to food. If a dose is forgotten, the patient should take it within 2 days of the scheduled dose and resume taking study therapy on her regular day. Two tablets of blinded study therapy should not be taken on the same day or within a 5 day period as this constitutes an overdose. Compliance with blinded study therapy will be assessed via tablet count and patient report, and should be reinforced at all visits. Sites are encouraged to contact individual patients whom they feel have compliance issues on an as-needed basis.

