Analysis of log-fraction of baseline value in biochemical markers will utilize the same model as BMD endpoints. Data will be back-transformed for presentation. Biomarkers will be analyzed using the per-protocol population.

Bone Biopsies and Health Resource Utilization and Meal Questionnaires

Bone biopsy, health resource utilization and meal questionnaire data will be summarized for each treatment group.

Major Cardiovascular & Cerebrovascular Events

Time to first major cardiovascular and cerebrovascular event will be summarized in tabular and graphical format by the Kaplan-Meier method.

Product: MK-0822

20

Protocol/Amendment No.: 018-04

Population Pharmacokinetics

Population PK analysis and/or PK/PD modeling may be performed. Details will be specified in a separate population PK/PD Statistical Analysis Plan.

Safety Analyses

The primary safety analysis will focus on adverse experiences, with special attention to the Other Non-serious Adverse Experiences mentioned in Sections 3.3.4 and 3.4.1.3. The analysis of adverse experiences will follow a multitiered approach. Safety will be performed using the All-Patients-as-Treated (APaT) population.

Multiplicity

The study will be terminated if the pre-specified number of events is seen for all 3 primary fracture endpoints. The final analysis will be performed at that time. Interim analyses will be performed for the DMC's safety review; the DMC will also monitor efficacy results in the formal efficacy interim analyses as detailed in Section 3.5.5.6 of the Data Analysis Section (DAS).

Multiplicity Due to Multiple Fracture Endpoints

This study is primarily designed to investigate the effect of odanacatib on morphometric vertebral, non-vertebral and hip fractures. To control the false positive error rate due to multiple fracture endpoints in the final analysis, a combination of a step-down closed-testing and Hochberg procedure [8] will be applied. First a step-down procedure will be utilized with the following order of clinical importance: (1) morphometric vertebral fractures, (2) hip and non-vertebral fractures. To control the false positive error rate for multiple tests for hip and non-vertebral fractures, a Hochberg procedure [8] will be used.

In the interim analyses, the trial will not be terminated unless strong evidence (significance) is seen for all 3 primary fracture endpoints, additional detail is provided in the DAS.

Multiplicity Adjustment for Secondary Endpoints

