
Product: MK-0822

52

Protocol/Amendment No.: 018-04

Summary of Efficacy Analyses:

A summary of the efficacy analyses performed in this study is in Table 3-10.

Table 3-10
 Efficacy Analyses

Efficacy Endpoint	Statistical Method	Analysis Approach	Additional remark
Morphometric Vertebral Fractures			
Time to first fracture	Life-table estimates for each time point	FAS + PP	PP only if >10% PVs.
Time to first fracture	Interval censored analysis (cloglog model)	FAS + PP	PP only if >10% PVs.
Time to first fracture	Summary of number (%) of patients with a fracture up to each time point	FAS + PP	PP only if >10% PVs.
Number of fractures	Summary of number (%) patients with 0, 1, 2, >2 fractures	FAS	
Clinical Fractures (Hip, Non-vertebral and Vertebral)			
Time to first fracture	Kaplan-Meier curve and estimates for each time point	FAS + PP	PP only if >10% PVs.
Time to first fracture	Cox proportional hazards model	FAS + PP	PP only if >10% PVs.
Number of fractures	Summary of number (%) patients with 0, 1, 2, >2 fractures	FAS	
Stature			
Change from baseline at each time point	Summary table and line plot over time.	FAS	
Stature loss of >1 cm	Summary of number (%) patients and logistic model	FAS	
Rate of stature loss	Mixed model with fixed effects for treatment, stratum, region, treatment-time and random intercept and slope.	FAS	
Bone Mineral Density Endpoints			
Percent change from baseline at all time points.	Summary table.	FAS	
Percent change from baseline at all time points.	Longitudinal approach and line plot of LS means over time	FAS	
Bone Biopsy Endpoints			
Bone biopsy measurements	Summary table.	FAS	

Product: MK-0822

54

Protocol/Amendment No.: 018-04

Efficacy Analyses (Cont.)

Efficacy Endpoint	Statistical Method	Analysis Approach	Additional remark
Qualitative abnormality [†]	Summary of number (%) of patients	FAS	
Biochemical Markers of Bone Resorption and Bone Formation			
Log-transformed fraction from baseline	Summary table of geometric mean percent change from baseline.	PP	
Log-transformed fraction from baseline	Longitudinal model and line plot of LS mean over time.	PP	Testing only for resorption markers.
Indices of Calcium and Mineral Homeostasis			
Log-transformed fraction from baseline	Summary table of geometric mean percent change from baseline.	PP	
Major Cardiovascular and Cerebrovascular Events			
Time to first event	Kaplan-Meier curve and estimates for each time point	FAS	
Health Resource Utilization Questionnaire			

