The number and percentage of patients with secondary diagnoses will be summarized by treatment group for each system organ class and preferred term, for terms with an incidence of at least 1% in one of the treatment groups. Similar summaries will be provided for all specific secondary diagnoses and for the number of patients with prior medications and for the number of patients with concomitant medications. Special attention will be paid to prior osteoporotic medications.

Study participants accounting will be examined by tabulation of the number of patients screened but not randomized (with the reason for not being randomized), the number of patients randomized, the number of patients completing the study, and the number of patients discontinuing the study early with the reasons for early discontinuation and the number of patients who discontinued treatment early with the reason for early termination. Since this is a pure Intention to Treat (ITT) study, patients are to be followed off-drug for the remainder of the study if they discontinue treatment early.

Definition of Compliance Measure

For each patient, two compliance measures will be calculated based on the prime therapy records provided in the eCRFs. The first one describes the compliance to treatment up to treatment discontinuation and the second during the complete study.

Compliance During the Treatment Period:

The compliance during the treatment period, until permanent discontinuation from treatment, will be defined as:

$$\begin{aligned} & \text{compliance during treatment period (\%)} \\ & = 100 * \frac{\text{actual number of days with double - blind treatment intake}}{\text{expected number of days with intake in treatment period}} \end{aligned}$$

The "actual number of days with double-blind treatment intake" refers to the number of days on which double-blind treatment was taken.

The "expected number of days with intake in treatment period" refers to the number of days during the treatment period on which a weekly tablet was to be taken, calculated as

Product: MK-0822

16

Protocol/Amendment No.: 018-04

the number of days from the study treatment start day to the date of the last treatment intake before the cut-off date for analysis divided by 7 (rounded upwards).

Compliance During the Complete Study:

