The per-protocol analysis set excludes patients and/or data points that represent clinically important deviations from the protocol-specified criteria, and so should not be considered a repetition of the inclusion and exclusion criteria defined in the protocol, but rather as a clinical assessment of protocol-specified deviations that may affect or confound the measures of efficacy. The per-protocol analysis will be performed as the primary approach for the biochemical marker data and may be performed as a secondary analysis for the primary endpoints (morphometric vertebral, hip and non-vertebral fractures). The per-protocol analyses for fractures will not be performed if less than 10% patients (included in the FAS approach) are protocol violators.

The listing of patients/data points who will not be included in the per-protocol analyses will be provided before frozen file.

The following rules will be applied to exclude patients/data points from the per-protocol analysis:

All Efficacy Analyses

1. Patient was <3 years postmenopause at baseline.
2. Missed >4 consecutive doses, or was <75% compliant with study medication before the biomarker measurement.

For fractures: Data will be excluded from the PP analysis from the time point onwards when >12 consecutive doses were missed, irrespective of the timing in the study. For time point more than 6 months (180 days) from start of prime therapy data will also be disregarded from the PP analysis when the total period off-drug (not necessarily consecutive doses) is more than 25% of the time in the study. Fractures

Product: MK-0822

32

Protocol/Amendment No.: 018-04

after this time point will be disregarded and the patient will be censored at the first time point where she is considered a protocol violator².

3. Patient had a history of primary parathyroid disease within 2 years prior to entry (not cured by parathyroidectomy), with elevated PTH or serum calcium greater than the upper limit of normal at baseline.
4. Patient has a history of secondary hyperparathyroidism.
5. Patient has a history of hypocalcemia (<8.5 mg/dL, corrected for albumin), accompanied by an elevated PTH at baseline (>65 pg/mL).
6. Patient has a baseline TSH <0.1 microIU/mL.
7. Patient has a history of a metabolic bone disorder, other than osteoporosis (examples include Paget's Disease of Bone, osteogenesis imperfecta, osteomalacia, renal osteodystrophy).

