8. Use of the following medications prior to randomization or concomitantly during the study (the doses and durations of specific treatments which will classify a patient as a protocol violator, based upon either prior or concomitant use, will be defined after data are available for review, but prior to unblinding for the first efficacy interim analysis). Patients/data points will be excluded from the start of the concomitant medication onwards.
 - anabolic steroids or glucocorticoids (≥ 5 mg/day prednisone or equivalent),
 - oral bisphosphonates (including alendronate, risedronate, clodronate, etidronate, ibandronate, or tiludronate),
 - I.V. bisphosphonates (including zoledronate, ibandronate, pamidronate),
 - cathepsin K inhibitor,
 - cyclosporine,
 - fluoride,
 - strontium,
 - PTH,
 - phenytoin, chemotherapy, heparin, or growth hormone,
 - estrogen \pm progestin (excluding topical applications), raloxifene, lasofoxifene, or other SERM, tamoxifen, tibolone, or an aromatase inhibitor,

² The number of missed consecutive doses was increased from 4 to 12 because the lower number was deemed overly stringent, as it equaled only 1 month of therapy, compared to approximately 3 months for 12 doses. In addition, it was felt that overall compliance with study medication was of greater importance after the first 6 months of treatment, as the effects of odanacatib on bone mineral density and bone strength (and hence fracture risk) have been shown to be time-dependent. Lower compliance during the first 6 months of the study is less likely to have a negative impact on the overall treatment effect, as fracture rates during this time period are more likely to be influenced by the patient's baseline level of risk, and yet to be altered by treatment.

Product: MK-0822

33

Protocol/Amendment No.: 018-04

- vitamin A (retinol and/or its esters); beta-carotene use is permitted,
- vitamin D (excluding study-provided concomitant vitamin D)

Biochemical Markers and Indices of Calcium and Mineral Homeostasis

Patients will not be included in the biochemical marker analyses for one or more of the reasons listed above. In addition, for the biochemical markers of bone resorption (u-NTx, s-CTx), a value will be excluded from the analysis if the last dose of study medication prior to the value is taken >7 days prior to the value, and for biochemical markers of bone formation (BSAP, P1NP) if the last dose of study medication is taken >30 days prior to the value.

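### The formally tested bone-resorption markers have only a per-protocol analysis; a supportive full-analysis-set analysis should be added and the per-protocol result labelled as an on-drug effect

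*Protocol*

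**What the plan says.** Section 2.1.2 (5) sets a randomized comparison as a secondary hypothesis: "Treatment with odanacatib decreases biochemical indices of bone resorption (s-CTx and u-NTx) compared to placebo". Section 3.5.5.3 gives the resorption markers their own Hochberg family at 5%, gated on morphometric vertebral fracture and tested from the earliest time point onwards. Table 3-10 confirms that this is a formal test, with the remark "Testing only for resorption markers".

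The analysis set is stated the same way throughout:

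- Section 2.7: "Biomarkers will be analyzed using the per-protocol population".
- Section 3.5.4: "The analyses of biochemical markers of bone turnover and formation will be performed using the per-protocol approach".
- Table 3-10 lists PP alone for the markers, and Table 4 in Appendix 6.7 is headed as a per-protocol analysis.
- Appendix 6.7, Description of Protocol Violations: "The per-protocol analysis will be performed as the primary approach for the biochemical marker data".

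Appendix 6.7 then says which values are lost: those preceded by more than 4 consecutive missed doses or by compliance below 75%, and those from the start of listed bone-active drugs onwards, including bisphosphonates, strontium and PTH. The doses and durations that count as violations are still to be defined. In addition, a resorption-marker "value will be excluded from the analysis if the last dose of study medication prior to the value is taken >7 days prior".

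Sections 3.2.3.9 and 3.2.3.9.1 keep women who stop blinded therapy in follow-up, and the marker schedule has no exemption for them.

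**The concern.** Every exclusion listed above depends on what happens after randomization, and each is plausibly linked to the marker itself. Resorption is expected to rise again once odanacatib is stopped or taken irregularly. Women who meet the excessive-bone-loss criterion are to stop blinded therapy and may be given alendronate, which lowers resorption. Removing such values means that the arms compared are no longer the arms randomized.

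The other efficacy endpoints have a counterweight. Fractures are analysed in the FAS with PP as support. BMD has a supportive run that includes values taken long after the last dose, added expressly for consistency with the fracture approach. The markers have neither. The gap cannot be put down to a separate document, because section 3.5 says that the amendment incorporates all details of the stand-alone SAP.

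What is at stake is the reported size of suppression, the figure that readers will compare with other agents. A hypothesis with its own alpha would have no estimate protected by randomization.

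**Working it through.** **The plan's own figure.** The protocol gives no sample size or power for the markers. The only figure for the 10% subset concerns BMD (section 3.5.5.4): 1,200 women, difference 1%, SD 4%, two-sided alpha 5%, power 99%. With 600 per arm, 1 / (4 × √(2/600)) = 4.33, and Φ(4.33 − 1.96) = 0.991. It reproduces, but it does not bear on the choice of analysis set.

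**Inputs for the illustration**

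- On-drug suppression s: about 70% for s-CTx and 60% for u-NTx, from the phase I data in section 3.1.5, used here as the per-protocol effect versus placebo.
- Share f of sampled odanacatib women who are off drug: not given in the documents. Assumed 5% to 40%.
- Off-drug women retain no suppression (assumption).

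**Formula.** The markers are analysed as the log fraction of baseline and back-transformed, so effects mix on the log scale:

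FAS suppression = 1 − exp[(1 − f) × ln(1 − s)] = 1 − (1 − s)^(1 − f)

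| f | s-CTx | u-NTx |
|---|---|---|
| 0 | 70.0% | 60.0% |
| 5% | 1 − 0.3^0.95 = 68.1% | 1 − 0.4^0.95 = 58.1% |
| 10% | 1 − 0.3^0.90 = 66.2% | 1 − 0.4^0.90 = 56.2% |
| 20% | 1 − 0.3^0.80 = 61.8% | 1 − 0.4^0.80 = 52.0% |
| 40% | 1 − 0.3^0.60 = 51.4% | 1 − 0.4^0.60 = 42.3% |

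**Rescue on placebo.** Suppose also that a share g = 5% of placebo women are on alendronate with 50% suppression (both assumptions). The log effect then shrinks by 0.05 × ln(0.5) = −0.035. At f = 20% the results become 60.5% and 50.3%, a further 1 to 2 points lower.

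**Significance.** 10% of 16,300 women is about 815 per arm. Take u-NTx at f = 40%, where the log difference is 0.6 × 0.916 = 0.55, and an assumed log SD of 1.0, the top of a 0.5 to 1.0 range. Then 0.55 / (1.0 × √(2/815)) is about 11, so power is above 99.9%. Attrition would lower the number sampled at later visits, but the margin is wide.

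**The case against.** The strongest case for the plan is that the objective speaks of the effect of treatment with odanacatib, an on-drug reading of a pharmacodynamic marker fits that wording, and the choice is stated consistently. That stands as a reason to keep the per-protocol analysis. It does not explain why a formally tested comparison has no as-randomized estimate beside it.

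Several stronger readings are tempting, and the documents do not support them:

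- A reader might size the gap from the 20% drop-out over 3 years in Table 3-12. That rate describes women who leave observation. They give no later values to a FAS either, so it says nothing about the share off drug but still sampled.
- A reader might infer that BMD is analysed as randomized and the markers alone are on-drug. The main BMD analysis also leaves out measurements more than 30 days after the last dose. What the markers lack is the supportive all-data run.
- A reader might take "Since this is a pure Intention to Treat (ITT) study" as fixing the marker analysis set. It stands in the participant-accounting text and explains off-drug follow-up.
- A reader might say that whole patients are dropped. The rules act largely on data points, and earlier valid values can stay in the model.
- A reader might argue that removing placebo women with high resorption inflates the contrast. By itself that would shrink it. Overstatement relative to the FAS comes from the alendronate suppression their later values would show.
- A reader might want the 7-day limit changed. Section 2.4.2.1 says "If a dose is forgotten, the patient should take it within 2 days of the scheduled dose", so a woman sampled on day 8 or 9, just before a permitted late dose, loses her value. This is a narrow case, and the documents report no effect at those days.

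**Conclusion.** The point holds as a gap in the analysis plan for a secondary endpoint. The only planned test of s-CTx and u-NTx uses a set defined by post-randomization behaviour, and no full-analysis-set result is foreseen. The direction, per-protocol suppression above the randomized effect, is probable but is an inference: it rests on suppression being lost off drug and on alendronate lowering resorption in rescued placebo women. The size cannot be fixed from the documents. Under the stated assumptions it runs from about 2 percentage points at 5% off drug, through 8 points at 20%, to 18 to 19 points at 40%.

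The significance conclusion is unlikely to change, and the fracture endpoints are untouched. The documents do not show that the per-protocol analysis must be replaced as the tested one.

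**What to change.** In sections 2.7 and 3.5.4, Table 3-10 and Appendix 6.7, add a pre-specified supportive FAS analysis of the markers. It should include all women in the 10% subset with at least one dose, a baseline value and a post-baseline value, as randomized, regardless of adherence, time since last dose or other therapy. Use the same longitudinal model, report the result beside the per-protocol one, and label the latter as an on-drug effect.

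Separately, ask the sponsor to reconcile the 7-day analysis limit in Appendix 6.7 with the late-dose allowance in section 2.4.2.1.

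The cost is wording in four places and one more run of a model already specified, on samples already scheduled. The reported suppression may look less favourable.
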